5.2. Selection of Study Population

Subjects will be screened, and the data collected will be reviewed by the principal investigator. Only those subjects who meet all the eligibility criteria will be enrolled. Approximately 72 healthy subjects are planned for enrollment. Up to 14 subjects may be qualified as replacements as described in Section 5.5.2. Thus, a maximum of 86 subjects will be exposed to study drugs and procedures during the study. Every effort will be made to maintain an approximate 50:50 male to female sex distribution.

5.2.1 Inclusion Criteria

Subjects who meet all the following inclusion criteria will be eligible to participate in the study:

1. Subject signs an IRB approved written informed consent and privacy language as per national regulations (e.g., Health Insurance Portability and Accountability Act authorization) before any study related procedures are performed.
2. Subject is a healthy man or woman, 18 to 55 years of age, inclusive, who has a body mass index of 18.5 to 29.9 kg/m², inclusive, at Screening.
3. Subject has normal medical history findings, clinical laboratory results, vital sign measurements, 12 lead electrocardiogram (ECG) results, and physical examination findings at Screening or, if abnormal, the abnormality is not considered clinically significant (as determined and documented by the investigator or designee).

4. Subject must have a negative test result for alcohol and drugs of abuse at screening and Check-in (Day -1).
5. Subject has a peripheral blood eosinophil count of ≥ 50 and ≤ 700 cells per microliter as measured by a standard hematology analyzer.
6. Female subjects must be of non-childbearing potential or, if they are of childbearing potential, they must: 1) have been strictly abstinent for 1 month before Check-in (Day -1) and agree to remain strictly abstinent for the duration of the study and for at least 1 month after the last application of study drug; OR 2) be practicing 2 highly effective methods of birth control (as determined by the investigator or designee; one of the methods must be a barrier technique) from at least 1 month before Check-in (Day -1) until at least 1 month after the end of the study.
7. Male subjects must agree to practice 1 highly effective method of birth control (as determined by the investigator or designee) from at least 1 month before Check-in (Day -1) until at least 1 month after the end of the study.
8. Subject is highly likely (as determined by the investigator) to comply with the protocol defined procedures and to complete the study.

5.2.2 Exclusion Criteria

Subjects who meet any of the following exclusion criteria will not be eligible to participate in the study:

1. Subject is taking any medication known to affect leukocyte population numbers.
2. Subject is anemic (i.e., with Hct or Hgb less than the lower limit of normal) or has any chronic condition(s) that may impact blood sample collection.
3. Subject has had previous exposure to the biologic mepolizumab or reslizumab.
4. Subject has a history of asthma.
5. Subject has a history of anaphylaxis from environmental exposures such as peanuts or bee stings.
6. Subject has an allergic history that includes urticaria, angioedema or respiratory coughing or bronchospasm.
7. Subject has a history of severe local reactions or generalized erythema from skin allergen testing.
8. Subject is anemic or has any chronic condition(s) that may impact blood sample collection.
9. Subject has used any prescription or nonprescription drugs (including aspirin or NSAIDs and excluding oral contraceptives and acetaminophen) within 14 days or 5

half-lives (whichever is longer) or complementary and alternative medicines within 28 days before the first dose of study drug.

10. Subjects are currently participating in another clinical study of an investigational drug or are have been treated with any investigational drug within 30 days or 5 half-lives (whichever is longer) of the compound.
11. Subject has used nicotine-containing products (e.g., cigarettes, cigars, chewing tobacco, snuff) within 6 weeks of Screening.
12. Subject has consumed alcohol, xanthine-containing products (e.g., tea, coffee, chocolate, cola), caffeine, grapefruit, or grapefruit juice within 48 hours of dosing. Subjects must refrain from ingesting these throughout the study.
13. Subject has any underlying disease or surgical or medical condition (e.g., cancer, human immunodeficiency virus [HIV], severe hepatic or renal impairment) that could put the subject at risk or would normally prevent participation in a clinical study. This includes subjects with any underlying medical conditions that put subjects at higher risk for coronavirus disease of 2019 (COVID-19) complications; per current Center for Disease Control and Prevention (CDC) recommendations this includes:
 - People with chronic lung disease or moderate to severe asthma
 - People who have serious heart conditions
 - People who are immunocompromised
 - Many conditions can cause a person to be immunocompromised, including cancer treatment, smoking, bone marrow or organ transplantation, immune deficiencies, poorly controlled HIV, and prolonged use of corticosteroids and other immune weakening medications
 - People with severe obesity (body mass index [BMI] of 40 or higher)
 - People with diabetes
 - People with chronic kidney disease undergoing dialysis
 - People with liver disease
14. Subject has any signs or symptoms that are consistent with COVID-19. Per current CDC recommendations this includes subjects with the symptoms cough or shortness of breath or difficulty breathing, or at least two of the following symptoms: fever, chills, repeated shaking with chills, muscle pain, headache, sore throat or new loss of taste/smell. In addition, the subject has any other findings suggestive of COVID-19 risk in the opinion of the investigator.
15. Subject tests positive for severe acute respiratory syndrome coronavirus 2 (SARS-CoV-2) by a molecular diagnostic test performed prior to admission.
16. Subject has known or suspected allergies or sensitivities to any study drug.

17. Subject has clinical laboratory test results (hematology, serum chemistry) at Screening that are outside the reference ranges provided by the clinical laboratory and considered clinically significant by the investigator.
18. Subject has a positive test result at Screening for HIV 1 or 2 antibody, hepatitis C virus antibodies, or hepatitis B surface antigen.
19. Subject is unable or unwilling to undergo multiple venipunctures for blood sample collection because of poor tolerability or poor venous access.
20. Female subjects are pregnant or lactating before enrollment in the study.
21. Subject is known to have, or is suspected to have, a parasitic infection.

5.3. Screening Failures

Subjects who sign and date the informed consent form but who fail to meet the inclusion and exclusion criteria are defined as screening failures. A screening log, which documents the subject initials and reason(s) for screening failure, will be maintained by the investigator for all screening failures. A copy of the log should be retained in the investigator's study files.

If a subject fails the screening process because of an abnormal laboratory result, they can receive a copy of the results upon request. The investigator will determine if follow-up for the abnormal laboratory result is needed and will encourage the subject to follow-up with his or her personal physician as appropriate. All subjects will be informed as to the reason(s) they are excluded from study participation, even if follow-up is not required. If a subject fails the screening process because of a positive test result for human immunodeficiency virus or hepatitis, the positive result will be reported to local health authorities as required by law.

5.4. Termination of Study or Investigational Site

5.4.1 Criteria for Termination of the Study

The study will be completed as planned unless one of the following criteria is satisfied that requires early termination of the study.

- New information regarding the safety or efficacy of the study drug(s) that indicates a change in the known risk profile for the study drug(s), such that the risk is no longer acceptable for subjects participating in the study.
- Significant violation of Good Clinical Practice (GCP) that compromises the ability to achieve the primary study objective or compromises subject safety.

5.4.2 Criteria for Termination of Investigational Site

The study site may be terminated if the site (including the investigator) is found in significant violation of GCP, the protocol, the contractual agreement, or is unable to ensure adequate performance of the study.

If the sponsor elects to terminate the study or the investigational site, a study-specific procedure for early termination will be provided by the sponsor; the procedure will be followed by the applicable investigational site during the course of termination.

5.5. Criteria for Subject Withdrawal

Subjects may withdraw from the study at any time at their own request, or they may be withdrawn by the investigator without the approval of the subject based on the investigator's clinical judgment. A subject is not required to provide a written request to withdraw from the study; however, a written request is required if a subject withdraws consent for his or her personal data to be used for study-related purposes.

A subject may be discontinued for any of the following reasons:

- AE: The subject has experienced an AE that, in the opinion of the investigator, requires early termination. The appropriate electronic case report form (eCRF) must be completed for each AE. If a subject is discontinued from the study due to an AE, the investigator is required to follow-up with the subject until the event resolves or becomes stable. If a subject dies during the study, the cause of death must be reported as a serious adverse event (SAE), with an outcome of death noted in the eCRF.
- Protocol Violation: The subject failed to meet protocol entry criteria or did not adhere to protocol requirements, and continued participation poses an unnecessary risk to the subject's health.
- Withdrawal by Subject: The subject (or other responsible individual [e.g., caregiver]) wishes to withdraw from the study in the absence of a medical need.

NOTE: Withdrawal due to an AE should not be recorded in the "voluntary withdrawal" category.

- Study Terminated by Sponsor: The sponsor, IRB, or other regulatory agency terminates the study.
- Pregnancy: The subject is found to be pregnant.

NOTE: If the subject is found to be pregnant, the subject must be withdrawn immediately. The pregnancy will be followed-up to term, and the outcome, including any premature termination will be recorded. All live births must be followed for a minimum of 30 days or until the first well-baby visit.

- Other.

NOTE: This category records withdrawals caused by an accidental or a medical emergency, unblinding, and other rare cases. The specific reason should be recorded in the comment space of the eCRF.

5.5.1 Handling of Withdrawals

The investigator may terminate a subject's study participation at any time during the study when the subject meets the criteria described in Section 5.5. In addition, a subject may discontinue his or her participation without giving a reason at any time during the study. Subjects will be informed that their participation in the study is voluntary, that refusal to participate will involve no penalty or loss of benefits to which the subject is otherwise entitled, and that the subject may discontinue participation at any time without penalty or loss of benefits to which the subject is otherwise entitled.

Should a subject's participation be discontinued, the primary reason for termination must be recorded. In addition, efforts should be made to perform all procedures scheduled for the early termination visit. Any data and samples collected before subject withdrawal will become the property of the FDA.

5.5.2 Replacement Subjects

Approximately 72 healthy subjects are planned for enrollment and randomized to 1 of 9 treatment groups. Up to 14 subjects may be qualified as replacements. Thus, a maximum of 86 subjects will be exposed to study drugs and procedures during the study.

A replacement algorithm will be pre-specified in the subject replacement plan to guide the unblinded contracted study clinic pharmacist to determine this while the rest of the staff and sponsor remain blinded. A maximum of 14 replacement subjects may be enrolled in the study, and replacement subjects (if needed) must complete the treatment period. A replacement subject will receive the same treatment as the subject being replaced.

5.6. Study Visits

5.6.1 Recruitment

Recruitment materials (e.g., internet, radio, and print advertisements, social media posts) will be approved by the local IRB before telephone screening. The sponsor is responsible for registration of the study on clinicaltrials.gov; however, this may not occur until the local IRB has approved the final study protocol.

5.6.1.1 Compensation

Subjects will be offered payment for Screening; however, if the results of their alcohol and drug screening tests are positive, they will not be compensated. Subjects who complete the entire study will receive payment according to the schedule provided in the informed consent form. No special incentives are offered. Final payment will not be released until all follow-up procedures have been completed and accepted by the investigator.

If a subject chooses to withdraw from the study prematurely, he or she will only be compensated for completed days. If subjects are withdrawn for medical reasons or if the study is halted temporarily or permanently, the subjects will receive compensation proportional to the time spent in the study. No compensation will be provided if a subject is dismissed from the study for noncompliance (e.g., improper conduct, ingesting alcohol and/or drugs [including recreational drugs], tampering with the study drug, consuming any prohibited foods or beverages).

If subjects are required to stay in the clinic for a longer period for safety reasons, they will be compensated at a rate proportional to the entire compensation for the study. If a subject becomes ill or physically injured because of participation in this study, the subject will be referred for treatment.

5.6.2 Screening

The following procedures and assessments will be performed at Screening (Day -21 to Day -2):

- Obtain informed consent/HIPAA authorization. The informed consent process will be performed by a clinical research nurse in a private room. The subject will be given unlimited time to ask questions regarding study participation, and each subject will be questioned to ensure their understanding.

After informed consent is obtained:

- Review inclusion/exclusion criteria to confirm subject eligibility
- Record demographic information
- Measure height, weight, and calculate body mass index
- Perform serology screening (HIV antigen/antibody [Ag/Ab] Combo 1/2, HepC antibody, HBsAg)
- Record medical history
- Perform alcohol and drug screening (amphetamines, barbiturates, benzodiazepines, cannabinoids, cocaine, alcohol, opiates, phencyclidine, propoxyphene, and methadone)

- Perform a serum pregnancy test (female subjects only)
- Perform FSH measuring (postmenopausal [i.e., without menses for two years] female subjects only)
- Record prior medications
- Monitor for AEs
- Perform clinical laboratory tests (hematology, serum chemistry, and urinalysis)
- Measure vital signs (blood pressure, heart rate, respiratory rate, and oral body temperature)
- Perform a safety 12-lead ECG
- Perform a complete physical examination
- Collect urine sample (3-5 mL) for other omic analyses (e.g., transcriptomics and metabolomics)

5.6.3 Study Periods

This is a randomized, placebo-controlled, single-dose, parallel arm study. Healthy subjects will be randomized to four dose groups (low, intermediate low, intermediate high, and high) of each drug (mepolizumab or reslizumab) or placebo. Subjects assigned to Groups A, B, E, and F will be randomized to remain in the study for 63 days and the remaining subjects (in Groups C, D, G, H, and I) will remain in the study for 123 days.

5.6.3.1 Check-in

The following procedures and assessments will be performed at Check-in (Day -1):

- Perform/review results from SARS-CoV-2 molecular diagnostic test
- Review inclusion/exclusion criteria to confirm subject eligibility
- Review medical history
- Perform alcohol and drug screening (amphetamines, barbiturates, benzodiazepines, cannabinoids, cocaine, alcohol, opiates, phencyclidine, propoxyphene, and methadone)
- Perform a serum pregnancy test (female subjects only)
- Admit subject to the study clinic
- Randomization (after completion of check-in procedures on Day -1 or just before dosing on Day 1)
- Record concomitant medications

- Monitor for AEs
- Perform clinical laboratory tests (hematology, serum chemistry, and urinalysis)
- Measure vital signs (blood pressure, heart rate, respiratory rate, and oral body temperature)
- Perform a safety 12-lead ECG
- Perform a comprehensive physical examination
- Collect whole blood for isolation of eosinophils (5 mL)
- Collect whole blood (5 mL) and process for plasma for proteomic and small-RNA transcriptomic analyses
- Collect urine sample (3-5 mL) for other omic analyses (e.g., transcriptomics and metabolomics)

5.6.3.2 Treatment

The following procedures and assessments will be performed during the treatment period according to the Schedules of Events (Table 9-1):

- Record concomitant medications
- Monitor for AEs
- Perform clinical laboratory tests
- Administer study drug according to the randomization schedule following all other pre-dose examinations and specimen collection
- Perform a complete or targeted physical examination
- Measure vital signs (blood pressure, heart rate, respiratory rate, and oral body temperature). If vital signs are scheduled at the same time as another event, vital signs will be measured after the ECG, but before blood sample collection
- Perform safety 12-lead or telemetered ECG monitoring. If scheduled for the same time, safety 12-lead or telemetered ECG monitoring will always be performed before vital sign measurement and blood sample collection
- Perform alcohol and drug screening (amphetamines, barbiturates, benzodiazepines, cannabinoids, cocaine, alcohol, opiates, phencyclidine, propoxyphene, and methadone)
- Collect urine sample (3-5 mL) for omic analyses (e.g., metabolomics)
- Collect PK blood samples (5 mL). There are no washout periods for this study

- Collect blood eosinophil blood samples (3.5 mL) for flow cytometry
- Collect whole blood (5 mL) for plasma proteomic and small RNA transcriptomic analyses
- Collect buffy coat for genomic analyses

5.6.4 Discharge (or Early Termination)

The following procedures and assessments will be performed before the subject is discharged from the study (Day 63 or Day 123) or at early termination according to Table 9-1:

- Perform a serum pregnancy test (female subjects only)
- Record concomitant medications
- Monitor for AEs
- Perform clinical laboratory tests (hematology, serum chemistry, and urinalysis)
- Measure vital signs (blood pressure, heart rate, respiratory rate, and oral body temperature)
- Perform a safety 12-lead ECG
- Perform a complete physical examination
- Measure height, weight, and calculate body mass index
- Perform alcohol and drug screening (amphetamines, barbiturates, benzodiazepines, cannabinoids, cocaine, alcohol, opiates, phencyclidine, propoxyphene, and methadone)
- Collect a single PK blood sample (5 mL)
- Collect whole blood eosinophil blood sample (3.5 mL) for flow cytometry
- Collect whole blood (5 mL) and process for plasma for proteomic and small RNA transcriptomic analyses
- Collect urine (3-5 mL) for omic analysis (e.g., transcriptomics and/or metabolomics)
- Remove IV catheter (if applicable)
- Discharge subject from the study clinic after completion of all study procedures

5.7. Study Procedures

5.7.1 Pharmacokinetic Assessments

5.7.1.1 Pharmacokinetic Sample Collection

Pharmacokinetic blood samples (5 mL) for determination of free mepolizumab or reslizumab concentration will be collected at the following time points:

- Day 1: 0 (pre-dose), 1, 4, 12, 24 h
- Day 2, 3, 4, 5, 6, 7, 8, 9, 10, 11, 12, 13, 14, 21, 28, 35, 42, 49, 56, 63, 93, 123

Blood samples will be collected by direct venipuncture or by inserting an IV catheter into the subject's forearm region. Each blood sample will be labeled with subject number, study number, study day, time point, event, and a barcode that matches that belonging to the subject.

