Approximately 72 healthy subjects are planned for enrollment. Up to 14 subjects may be qualified as replacements. Thus, a maximum of 86 subjects will be exposed to study drugs and procedures during the study. Every effort will be made to maintain an approximate 50:50 male to female sex distribution.

Recruitment materials (e.g., internet, radio, and print advertisements, social media posts) will be approved by the local Institutional Review Board (IRB, i.e., Advarra) before telephone screening. Subjects will be offered payment for Screening and participation in the study, but no special incentives are offered.

Study Drugs, Dosage, and Route of Administration:

Nucala (mepolizumab) 100 mg/vial solution will be obtained. For the low (3 mg), low intermediate (6 mg) high intermediate (12 mg) and high doses (24 mg), the drug will be measured and reduced to the target dose (Table 5-1). The target dose will be administered subcutaneously in the upper arm.

Cinqair (reslizumab) 10 mg/mL solution in single-use vials will be obtained. For all doses, the drug will be measured and reduced to the target dose (Table 5-1). The target dose will be dispensed into an infusion bag containing 50 mL of 0.9% Sodium Chloride Injection, USP. The diluted solution of reslizumab will be administered intravenously over maximum 30 minutes. Infusion time will vary depending on the total volume to be infused as based on patient weight. The low dose will be 0.1 mg/kg, the low intermediate dose will be 0.2 mg/kg, the high intermediate dose will be 0.4 mg/kg and the high dose will be 0.8 mg/kg.

For all drugs, doses lower than the clinical dose will be used in this research study. A single dose of the assigned study drug will be administered to each subject during the treatment period.

Study Drugs

- Nucala (Mepoluzimab)
- Cinqair (Reslizumab)

**Reference Drug,
Dosage, and Route
of Administration:**

Subjects administered placebo will received either a placebo subcutaneous injection or placebo IV infusion. A placebo subcutaneous injection or equal volume and comparable pH to the diluent for high dose mepolizumab will be injected into upper arm subcutaneously for 4 subjects in the placebo treatment arm. A placebo IV infusion of equal volume and comparable pH to the diluent for high dose reslizumab will be administered to 4 subjects in the placebo treatment arm.

Inclusion Criteria:

Subjects who meet all the following inclusion criteria will be eligible to participate in the study:

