5.7.2.1.2 Exploratory PD Biomarkers

Exploratory PD biomarkers will be evaluated using plasma proteomics and small RNA transcriptomics. Whole blood samples (6 mL) will be collected at the following time points:

- Day -1 (check-in)
- Day 1: 0 (pre-dose), 0.5, 1, 2, 3, 4, 6, 9, 12, 18, 24 h
- Day 2, 3, 4, 5, 6, 7, 8, 9, 10, 11, 12, 13, 14, 21, 28, 35, 42, 49, 56, 63, 93, 123

Blood samples will be collected by direct venipuncture or by inserting an IV catheter into the subject's forearm region. Each blood sample will be labeled with subject number, study number, study day, time point, event, and a barcode that matches that belonging to the subject. All blood samples will be processed for preparation of plasma.

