5.8.1 Treatments Administered

On Day 1, subjects will receive 1 of the following 9 treatments according to the randomization schedule:

- Treatment Group A: Mepolizumab 3 mg, SC
- Treatment Group B: Mepolizumab 6 mg, SC
- Treatment Group C: Mepolizumab 12 mg, SC
- Treatment Group D: Mepolizumab 24 mg, SC
- Treatment Group E: Reslizumab 0.1 mg/kg, IV
- Treatment Group F: Reslizumab 0.2 mg/kg, IV

- Treatment Group G: Reslizumab 0.4 mg/kg, IV
- Treatment Group H: Reslizumab 0.8 mg/kg, IV
- Treatment Group I: Placebo, (4 subjects receive SC and 4 subjects receive IV)

Study drugs will be administered by a clinical research nurse on the study clinic floor at the subject's bedside. The pharmacist and investigator will be available if needed during study drug administration.

Note: Reslizumab must be given as an intravenous infusion only. Do not administer as an intravenous push or bolus.

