4.2. Secondary Endpoints

- Area under the curve (AUC) of mepolizumab and reslizumab from time zero to infinity (AUC_{0-inf})
- Maximum concentration (C_{max}) of mepolizumab and reslizumab
- Model parameter estimates for mepolizumab and reslizumab exposure-response models (exposure parameter versus AUEC_{0-t} or ΔEosinophil_{dec, max})

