Attachment A. Pharmacokinetic, Pharmacodynamic, and Biomarker Sample Collection Schedule

Pharmacokinetic Sample Collection

Pharmacokinetic blood samples (5 mL) for determination of mepolizumab and reslizumab concentration will be collected and processed for serum at the following time points:

- Day 1: 0 (pre-dose), 1, 4, 12, and 24 h (0 h, Day 2)
- Day 3, 4, 5, 6, 7, 8, 9, 10, 11, 12, 13, 14, 21, 28, 35, 42, 49, 56, 63, 93, and 123

Blood samples will be collected by direct venipuncture or by inserting an IV catheter into the subject's forearm region. Each blood sample will be labeled with subject number, study number, study day, time point, event, and a barcode that matches that belonging to the subject.

Pharmacodynamic Sample Collection

Blood samples (5 mL) for primary pharmacodynamic biomarker (eosinophils) assessment will be collected at the following time points:

- Screening (Day -21 to -2)
- Day -1 (check-in)
- Day 1: 0 (Pre-dose), 24 h (0 h, Day 2)
- Day 3, 4, 5, 6, 7, 8, 9, 10, 11, 12, 13, 14, 21, 28, 35, 42, 49, 56, 63, 93, and 123

Blood samples will be collected by direct venipuncture or by inserting an IV catheter into the subject's forearm region. Each blood sample will be labeled with subject number, study number, study day, time point, event, and a barcode that matches that belonging to the subject.

Exploratory PD Biomarkers

Exploratory PD biomarkers will be evaluated using plasma proteomics and small RNA transcriptomics. Whole blood samples (5 mL) will be collected and processed for plasma at the following time points:

- Day -1 (check-in)
- Day 1: 0 (pre-dose), 0.5, 1, 2, 3, 4, 6, 9, 12, 18 and 24 h (0 h, Day 2)
- Day 3, 4, 5, 6, 7, 8, 9, 10, 11, 12, 13, 14, 21, 28, 35, 42, 49, 56, 63, 93, and 123

Blood samples will be collected by direct venipuncture or by inserting an IV catheter into the subject's forearm region. Each blood sample will be labeled with subject number, study number, study day, time point, event, and a barcode that matches that belonging to the subject. All blood samples will be processed for preparation of plasma.

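### Reslizumab Cmax is a secondary endpoint, but no PK sample is planned at the end of the IV infusion: the first post-dose sample is at 1 h, after an infusion of at most 30 minutes

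*Protocol*

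**What the plan says.** Protocol section 4.2 makes the level and spread of Cmax and AUC at each dose a secondary endpoint for both drugs. SAP section 4.2 likewise lists the maximum concentration "of mepolizumab and reslizumab". Protocol section 5.7.1.3 defines Cmax as the observed peak, so it is not modelled or back-extrapolated.

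Reslizumab is IV only (protocol section 5.8.1: "Note: Reslizumab must be given as an intravenous infusion only"). On its duration, the protocol synopsis (study drugs, dosage and route) says: "The diluted solution of reslizumab will be administered intravenously over maximum 30 minutes". It adds: "Infusion time will vary depending on the total volume to be infused as based on patient weight".

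Protocol section 5.7.1.1 gives one PK schedule for both routes: "Day 1: 0 (pre-dose), 1, 4, 12, 24 h", then later days. SAP Attachment A gives the same Day 1 times. The layout of protocol Table 9-1 could not be read reliably, so this point rests on the section text.

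Blood for the exploratory proteomic and small-RNA work is drawn more often (protocol section 5.7.2.1.2): "Day 1: 0 (pre-dose), 0.5, 1, 2, 3, 4, 6, 9, 12, 18, 24 h". That draw goes into EDTA tubes for plasma (section 5.7.2.2.2), whereas PK samples are clotted for serum (section 5.7.1.2).

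**The concern.** After an IV infusion the concentration is expected to peak when the infusion stops, here at 30 minutes or sooner. A schedule whose first post-dose PK sample is at 1 h cannot record that peak, however well it is followed. The reslizumab Cmax that is reported will be the highest concentration from 1 h onward.

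The study exists to inform the design of later PK and PD similarity studies. A later study that samples at end of infusion would measure a different quantity from the one summarised here, and its designers might not notice. Protocol section 5.9.6.2 explains the interest in Cmax by reference to subcutaneous dosing. Neither document says why the same sampling times suit the IV drug. Using actual sampling times, as that section plans, does not recover a peak that was not sampled.

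**Working it through.** The plan states no expected Cmax, half-life or Cmax variability, so there is no figure of its own to reproduce. The timing comes from the documents; every kinetic value below is an assumption.

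**1. Gap between end of infusion and first post-dose sample.** Let D be the infusion duration and g the gap.
- If time 0 is the start of infusion, g = 1 h − D. With D = 30 min, g = 0.5 h. With D = 20 min (assumed), g = 0.67 h.
- If time 0 is the end of infusion, g = 1 h.
- The documents do not say which applies. Either way g is at least 0.5 h.

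**2. Shortfall in observed Cmax.** Let a fraction f of the end-of-infusion concentration decline with half-life t, the rest being flat over the first hour. Then shortfall = f × (1 − 2^(−g/t)).

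| f, t (assumed) | g = 0.5 h | g = 0.67 h | g = 1 h |
|---|---|---|---|
| 0.3, 24 h | 0.43% | 0.57% | 0.85% |
| 0.5, 6 h | 2.8% | 3.7% | 5.5% |
| 0.5, 2 h | 8.0% | 10.3% | 14.6% |

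For example, 0.5 × (1 − 2^(−0.5/2)) = 0.5 × 0.159 = 8.0%.

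**3. Sensitivity to the model.** For a two-phase infusion model, the concentration at or after the end of infusion is the sum over phases of A/(kD) × (1 − e^(−kD)) × e^(−k(time − D)). Here A is the share of a phase and k = ln 2 / half-life. With a fast share of 30-70%, a terminal half-life of 20 days and D = 30 min, the shortfall at 1 h is:
- 0.3-2.0% for a fast half-life of 12-48 h;
- 1.7-3.9% for 6 h;
- 4.6-19.5% for 1-2 h.

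**4. Is Cmax simply the 1 h value?** Not necessarily. Take f = 0.3, t = 24 h and g = 0.5 h.
- C(1 h) = 0.7 + 0.3 × 2^(−0.5/24) = 0.9957.
- C(4 h) = 0.7 + 0.3 × 2^(−3.5/24) = 0.9712, about 2.5% lower.
- With an assumed assay CV of 10%, z = 0.025/(0.10 × √2) = 0.17, so the 4 h reading exceeds the 1 h reading in about 43% of subjects.

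At the fast end (f = 0.5, t = 2 h) the values are 0.920 and 0.649. The 4 h value is about 30% lower, and the 1 h sample would nearly always be the maximum.

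**5. AUC.** In units of the initial concentration, the area in the first hour is at most 1 h. With a terminal half-life of 20 days (480 h) and f = 0.5, t = 2 h, total AUC is about 0.5 × 2/ln 2 + 0.5 × 480/ln 2 = 348 h. The whole first hour is then under 0.3% of AUC.

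**6. Would a fixed 0.5 h sample be enough?** For D = 30 min it captures the peak. For D = 20 min, the model in step 3 leaves a shortfall of 0.1-0.7% (fast half-life 12-48 h), 0.6-1.3% (6 h) or 1.6-7.4% (1-2 h). A sample tied to the actual end of infusion removes it in every case.

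**The case against.** A reader might infer that reslizumab Cmax will be materially understated. The documents do not support that, because they give no early kinetics. Under slow decline the loss is a few percent or less. It exceeds about 5% only if the early decline is fast (half-life of about 6 h or less), or if time 0 is the end of infusion and the half-life is about 12 h or less. A reader might also infer that Tmax is fixed at 1 h and that Cmax is the 1 h value in nearly every subject. Step 4 shows that this fails when decline is slow. In that case, taking the largest of several noisy readings pushes Cmax upward, against the shortfall.

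Precision is also limited. With 8 subjects per arm and an assumed Cmax CV of 20%, the log-scale SD is 0.198. The 90% interval for a geometric mean is exp(±1.895 × 0.198/√8), about −12% to +14%. Most of the assumed shortfalls lie inside that. The primary endpoints are eosinophil measures, and the SAP's exposure-response models use dose or AUC, so IV Cmax is only summarised descriptively. All of this stands and limits the weight of the point.

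A further argument is that a common proportional loss leaves the CV unchanged and cancels in a test-to-reference ratio. That holds only if the gap is common. The protocol says infusion time varies, though not by how much. Weight alone may matter little: at 0.8 mg/kg and 10 mg/mL, each extra 10 kg adds 0.8 mL to a 50 mL bag, or 1.6%. But the protocol sets only an upper limit on duration, and the endpoint includes the level of Cmax as well as its spread. Imprecision does not remove a sampling gap, and the planned data cannot show how large its effect was.

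**Conclusion.** The point holds as a gap in sampling, not as a demonstrated bias of material size. Following the plan exactly, the end-of-infusion peak is unsampled in all 32 reslizumab subjects (4 groups of 8), observed Tmax is bounded below by 1 h, and the delay after infusion is not standardised.

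The shortfall is about 0.4-8% for a 0.5 h gap, if 30-50% of the initial concentration declines with a half-life of 2-24 h. It is larger if the gap is longer or the decline faster, and negligible if the early decline is slow. Long sampling, to Day 63 or 123, suggests slow elimination but says nothing certain about early distribution. Mepolizumab, given subcutaneously, is not affected. The right label is a cheap improvement to a stated secondary endpoint.

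**What to change.** For the IV groups:
- Add one PK serum tube at the actual end of infusion. Use the scheduled 0.5 h draw where the times coincide. A separate tube is needed because that draw is EDTA plasma and PK is measured in serum.
- State whether time 0 is the start or the end of infusion.
- Record actual infusion start and stop times for each subject.
- List the sample in protocol section 5.7.1.1 and SAP Attachment A, and align Table 9-1.

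The cost is one extra 5 mL tube and one assay for about 36 IV subjects (32 reslizumab plus 4 IV placebo), before any replacements. Including the IV placebo subjects keeps procedures the same within the IV route. Using the existing draw means no extra visit and at most a small shift in its time.

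If sampling cannot change, the SAP should say that reslizumab Cmax is the highest concentration from 1 h onward, not the end-of-infusion peak, and report it alongside actual infusion durations. That needs text and recorded infusion times, but no extra blood.
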